2.4.3 Safety

Adverse Events

Adverse Events will be coded using the most recent version of Medical Dictionary for Regulatory Activities (MedDRA) coding. All AEs will be presented based on system organ class and preferred terms.

When reporting the trial results the EAC evaluation will be employed. All discrepancies between EAC and the investigators' classification of the CV events will be listed by event.

A Treatment Emergent Adverse Event (TEAE) is defined as an event that has onset date on or after the first day of exposure to randomised treatment and no later than 7 days after the last day of randomised treatment.

TEAEs are summarised descriptively whereas AE's not defined as treatment emergent are presented in listings. The summaries of TEAEs are made displaying the number of subjects with at least one event, the percentage of subjects with at least one event, the number of events and the event rate per 100 years. These summaries are done by seriousness, severity, relation to insulin treatment, relation to device, withdrawal due to AEs and outcome.

Furthermore summary tables based on system organ class and preferred terms are made for:

- all TEAEs
- serious TEAEs
- possibly or probably related TEAEs
- severe TEAEs
- TEAEs with preferred term that are experienced by at least 5% of the subjects in any treatment arm or by at least 5% of all subjects

Hypoglycaemic episodes

Hypoglycaemic episodes are recorded by subjects in their trial diaries throughout the trial. The information collected includes PG before treating the episode and whether the subject was able to treat him/herself. This information is used by Novo Nordisk A/S to classify an episode according to the confirmed hypoglycaemia definition and the ADA definition (severe, documented symptomatic, asymptomatic, probable symptomatic and relative) as further detailed in the protocol.

A hypoglycaemic episode is defined as treatment emergent if the onset of the episode is on or after the first day of exposure to randomised treatment and no later than 7 days after the last day of randomised treatment. A hypoglycaemic episode that has time of onset between 00:01 and 05:59 a.m. (both included) is considered to be nocturnal.

Data on treatment emergent hypoglycaemic episodes are presented in terms of the number of subjects with at least one event (N), the percentage of subjects with at least one event (%), the number of events (E) and the event rate per 100 years (R). Separate summaries are made by severity considering all confirmed hypoglycaemic episodes, confirmed hypoglycaemic episodes in the maintenance period, nocturnal confirmed hypoglycaemic episodes, nocturnal confirmed hypoglycaemic episodes in the maintenance period and the ADA classification of hypoglycaemia.

The number of treatment emergent severe, confirmed, confirmed in the maintenance period, nocturnal confirmed hypoglycaemic episodes and nocturnal confirmed in the maintenance period will be analysed using a negative binomial regression model with a log-link function and the logarithm of the time period for which a hypoglycaemic episode is considered treatment emergent as offset. The model will include treatment, anti-diabetic therapy at screening and sex as fixed factors, and age as covariate. If the number of severe or nocturnal confirmed hypoglycaemic episodes is too small for statistical analysis, then these analyses may not be performed.

Fundoscopy/fundus photography

Fundoscopy and fundus photography findings will be summarised descriptively including summaries of the change from baseline.

EKG

- EKG 12-lead findings will be summarised descriptively including summaries of the change from baseline.

Physical examination

- Physical examination should include:
- head, ears, eyes, nose, throat, neck
- respiratory system

- CV system
- gastrointestinal system incl. mouth
- musculoskeletal system
- central and peripheral nervous system
- skin

The physical examination measurements and their change from baseline will be summarised descriptively.

Vital signs

Vital signs include diastolic blood pressure, systolic blood pressure and pulse findings will be summarised descriptively including summaries of the change from baseline.

Laboratory safety parameters

The following laboratory assessments are performed:

- haematology (haemoglobin, leucocytes, thrombocytes, haematocrit, differential counts and erythrocytes)
- biochemistry (creatinine, total protein, ALT, AST, AP, sodium, potassium, albumin, total bilirubin)
- lipid profile (LDL, HDL, triglycerides and total cholesterol)
- urinary albumin-to-creatinine ratio assess in spot urine
- urine by sticks (tests for blood, protein and ketones)

Insulin antibodies

Individual laboratory values will be compared to their relevant reference range (when existing) and flagged as being below or above the range. Change from baseline will be summarised descriptively.

Change from baseline in lipid endpoints after 26 weeks of treatment will be analysed separately using an ANOVA method with treatment, anti-diabetic therapy at screening and sex as fixed factors, and age and baseline value as covariates.

Insulin degludec specific antibodies, insulin aspart specific antibodies, and cross-reacting antibodies will be illustrated using descriptive statistics and graphs.

Insulin dose

Prescribed and actual insulin dose per day and separately for morning and evening dose will be recorded. The respective insulin doses will be summarised descriptively according to regimen as dose in units and units/kg per week.

Body weight

In addition to the confirmatory statistical analysis after 26 weeks of treatment, body weight will summarised descriptively including summaries of the change from baseline.

Other assessments

The results from the blood pregnancy test will be presented in listings using the Safety Analysis Set.

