#### **4.2.3.2 Safety**

- Incidence of treatment emergent adverse events (TEAEs) during 26 weeks of treatment
- Number of treatment emergent hypoglycaemic episodes according to the American Diabetes Association (ADA) definition during 26 weeks of treatment
- Number of treatment emergent confirmed hypoglycaemic episodes in the maintenance period (from week 16 to end of treatment, including 1 week follow-up)
- Number of treatment emergent nocturnal (00:01-05:59) confirmed hypoglycaemic episodes in the maintenance period (from week 16 to end of treatment, including 1 week follow-up)
- Change from baseline in clinical evaluation during 26 weeks of treatment
  - Physical examination
  - Fundoscopy/fundus photography
  - 12-lead ECG
  - Vital signs
- Change from baseline in central laboratory assessments during 26 weeks of treatment
  - Haematology (haemoglobin, leucocytes, thrombocytes, haematocrit, differential counts and erythrocytes)
  - Biochemistry (creatinine, total protein, alanine aminotransferase (ALT), aspartat aminotransferase (AST), alkaline phosphatase (AP), sodium, potassium, albumin, and total bilirubin)
  - Lipid profile (low density lipoproteins (LDL), high density lipoproteins (HDL), triglyceride and total cholesterol)
  - Urinary albumin/creatinine ratio assessed in spot urine
  - Urine by sticks (tests for blood, protein and ketones)
  - Insulin antibodies
- Insulin dose after 26 weeks of treatment

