## 6 Trial population

### 6.1 Number of subjects

Country planned to participate: China

Number of subjects planned to be screened (i.e. documented informed consent): 767

Number of subjects planned to be randomised/started on trial product(s): 537

Number of subjects expected to complete the trial: 450

A screening failure rate of 30 % and a withdrawal rate of 15% is anticipated for this trial.

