1.2 Scope of the statistical analysis plan

This SAP is based on the statistical analyses in the protocol 'A trial comparing efficacy and safety of insulin degludec/insulin aspart and BIAsp 30 in subjects with type 2 diabetes', version 4.0, 31 May 2017. This SAP includes the definition of last observed value (LOV), leaves out the mean PG at baseline as covariate in the analysis for the 2-point profiles, and clarifies the convergence to mmol/mol of a very low HbA1c measured in %.

Changes to the statistical methods proposed in the SAP and the reason for the change must be reported in the clinical trial report (CTR).

2 Statistical considerations

Novo Nordisk will analyse and report data from all sites together.

Analyses of all endpoints will be based on the Full Analysis Set (FAS). The primary efficacy analysis will be repeated on the Per Protocol (PP) analysis set in accordance with the Committee for Proprietary Medicinal Products (CPMP) Points to Consider¹.

Secondary confirmatory and supportive efficacy endpoints and patient reported outcome endpoints will be summarised using the FAS. Safety endpoints will be summarised using the Safety Analysis Set (SAS).

The impact of protocol deviations and outliers may be investigated further in sensitivity analyses if deemed relevant.

The primary objective of this trial is to confirm efficacy of the investigational product in terms of glycaemic control as assessed by HbA_{1c}. If efficacy of the investigational product can be confirmed as assessed by comparing the mean HbA_{1c} treatment difference to a non-inferiority limit of 0.4%, the trial also aims to show superiority of the investigational product over the comparator for a number of confirmatory secondary endpoints. The family-wise type I error rate will be controlled in the strong sense using a hierarchical (fixed sequence) testing procedure. This is based on a priori ordering of the null-hypotheses and testing them in this order using the two-sided 95% confidence interval approach until an insignificant result appears. The effect is that superiority only will be confirmed for endpoints where all previous null-hypotheses have been rejected.

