In addition, if non-inferiority can be confirmed and the 95% confidence interval for the mean HbA_{1c} treatment difference not only lies entirely below 0.4% but also below zero this will be considered as evidence of superiority of the investigational product over the comparator in terms of change from baseline in HbA_{1c} after 26 weeks of treatment.

Only endpoints derived after 26 weeks of treatment will be analysed statistically. Missing values will be imputed using the Last Observation Carried Forward (LOCF) method. LOCF has been a standard approach in diabetes trials for many years, and was used as the primary analysis in all degludec phase 3a trials. LOCF is considered to be an appropriate method in the context of treat-to-target trials, where subjects after withdrawal typically continue their therapy using commercially available insulin. In previous treat-to-target trials with degludec LOCF has generally provided similar results to alternative methods to handle missing data, such as repeated measures models and completer analyses. In this trial, similar sensitivity analyses will be made to examine the robustness of the LOCF method. All endpoints will be summarised descriptively at each visit by treatment and in total using observed data. After 26 weeks of treatment, descriptive statistics will be presented based both on observed and Last Observed Value (LOV) data, which corresponds to LOCF imputed data. Endpoints that are analysed untransformed and endpoints that are not formally analysed are summarised by the arithmetic mean, standard deviation (SD), median, and minimum and maximum value. Endpoints that are analysed log-transformed are summarised by the geometric mean, CV, median, minimum and maximum value.

LOCF imputed data will be used as the basis for plotting data if not otherwise specified.

Presentation of results from a statistical analysis will include the estimated mean treatment effects (least-squares means [LSMeans]) for absolute values and change from baseline if applicable. Estimated mean treatment differences (or ratios) will be presented together with two-sided 95% confidence intervals for all endpoints analysed statistically. P-values will only be presented for the primary and the confirmatory secondary endpoints for which formal statistical testing will be performed. The other endpoints are considered supportive and explorative in nature and no p-values will be presented.

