The number of confirmed hypoglycaemic episodes will be analysed using a negative binomial regression model with a log-link function and the logarithm of the time period in which a hypoglycaemic episode is considered treatment emergent as offset. The model will include treatment, anti-diabetic therapy at screening and sex as fixed factors, and age as covariate.

Number of treatment emergent nocturnal confirmed hypoglycaemic episodes

A hypoglycaemic episode that has time of onset between 00:01 and 05:59 a.m. (both included) will be considered nocturnal.

The number of treatment emergent nocturnal confirmed hypoglycaemic episodes will be analysed using a negative binomial regression model with a log-link function and the logarithm of the time period in which a hypoglycaemic episode is considered treatment emergent as offset. The model will include treatment, anti-diabetic therapy at screening and sex as fixed factors and age as covariate.

Change from baseline in body weight

Body weight is assessed at trial site. Change from baseline in body weight after 26 weeks of treatment will be analysed using an ANOVA method with treatment, anti-diabetic therapy at screening and sex as fixed factors, and age and baseline body weight as covariates.

Responder without hypoglycaemic episodes

Responder without hypoglycaemic episodes is a dichotomous endpoint (responder/non-responder) that is defined based on whether a subject has met the ADA HbA_{1c} target (< 7%) after 26 weeks of treatment without treatment emergent confirmed hypoglycaemic episodes during the last 12 weeks of treatment or within 7 days after last randomised treatment. The endpoint will only be defined for subjects that have been exposed to the investigational product or its comparator for at least 12 weeks.

Responder analysis will be based on a logistic regression model using treatment, anti-diabetic therapy at screening and sex as fixed factors, and age and baseline HbA_{1c} as covariates.

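### The two maintenance-period hypoglycaemia models set about 11 weeks of events against about 27 weeks of exposure, so a completer's modelled rate is 59% too low

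*SAP*

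**What the plan says.** SAP section 2.4.3 (Hypoglycaemic episodes) names five counts in one sentence: severe, confirmed, confirmed in maintenance, nocturnal confirmed, and nocturnal confirmed in maintenance. All five go into a negative binomial model with "the logarithm of the time period for which a hypoglycaemic episode is considered treatment emergent as offset". Protocol section 17.4.2.2 has the same sentence.

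Treatment emergent is a defined term. SAP section 2.4.3 states: "A hypoglycaemic episode is defined as treatment emergent if the onset of the episode is on or after the first day of exposure". The window closes 7 days after the last day of randomised treatment, and nothing restricts it to maintenance.

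The maintenance period is defined only in Protocol section 4.2.3.2: "Number of treatment emergent confirmed hypoglycaemic episodes in the maintenance period (from week 16 to end of treatment, including 1 week follow-up". The nocturnal endpoint has the same window. The SAP uses the term without defining it. Neither document gives a separate exposure time for these models, or a rule for subjects who leave before week 16.

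On reporting, the SAP's Statistical considerations (section 2) say: "Presentation of results from a statistical analysis will include the estimated mean treatment effects (least-squares means [LSMeans]) for absolute values". On status they say: "The other endpoints are considered supportive and explorative in nature and no p-values will be presented".

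**The concern.** A log-time offset turns a count into a rate only if it measures the time in which the counted events could occur. Here the count starts at week 16 and the offset starts at first dose. Sixteen weeks in which no event can count enter the denominator. Subjects with no treatment-emergent time after week 16 enter as zero counts with positive exposure.

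Two things follow:

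- **Absolute rates.** If model-based rates are reported, the maintenance rate will sit well below the whole-period rate in the same arm even when the true rate is constant. A reader could take this for fewer episodes once titration has settled.
- **Treatment comparison.** If early withdrawal differs by arm, the surplus denominator differs too, and the rate ratio moves.

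**Working it through.** The documents state no maintenance exposure or rate, so there is no figure of theirs to reproduce.

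**Inputs from the documents**

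- Treatment period: 26 weeks (Protocol section 5.3).
- Treatment-emergent window: first exposure to last treatment day + 7 days (SAP section 2.4.3).
- Maintenance window: week 16 to end of treatment + 1 week (Protocol section 4.2.3.2).
- Withdrawal: "a withdrawal rate of 15% is anticipated for this trial" (Protocol section 6.1), with no split by arm or time.

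**Completer.** Let T be the time in the offset and M the time in which events can count. With true rate λ the expected count is λM. The model reports a rate per unit of T, so modelled rate / true rate = M/T.

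- T = 26 + 1 = 27 weeks
- M = 26 − 16 + 1 = 11 weeks
- M/T = 11/27 = 0.407, so the rate is 59.3% too low (the correct rate is 27/11 = 2.45 times larger)

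If everyone completes, the two offsets differ by the constant log(27/11). Only the intercept changes, and the rate ratio is the same under either.

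**Early leavers**

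- Stop at week 20: T = 21, M = 5, 5/21 = 0.24, 76% too low.
- Stop at week 16: T = 17, M = 1, 1/17 = 0.06, 94% too low.
- Stop at or before week 15: M = 0 but T > 0.

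**Planned 15% withdrawal, assumed uniform over 26 weeks**

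- Mean T = 0.85 × 27 + 0.15 × 14 = 25.05 weeks
- Mean M = 0.85 × 11 + 0.15 × (11²/2)/26 = 9.70 weeks
- 9.70/25.05 = 0.387, so 61.3% too low. For 5% to 25% withdrawal the range is 59.9% to 62.8%.

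**Simulated negative binomial fits.** These inputs are assumptions and are not in the documents: true rate 6 per year, rate ratio 1, dispersion 2, 358/179 subjects, early leavers uniform over weeks 0–16, 5% of the rest leaving uniformly over weeks 16–26, 500 trials per scenario. Shift means the rate ratio under the offset as written divided by the ratio under the maintenance offset.

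| Leaving before week 16, IDegAsp / BIAsp 30 | BIAsp 30 rate, as written | BIAsp 30 rate, maintenance offset | Shift |
|---|---|---|---|
| 0% / 0% | 2.38 | 5.95 | 1.000 |
| 10% / 10% | 2.24 | 5.95 | 1.000 |
| 5% / 15% | 2.17 | 5.97 | 1.067 |
| 15% / 5% | 2.33 | 5.99 | 0.935 |
| 7.5% / 12.5% | 2.23 | 6.02 | 1.033 |
| 12.5% / 7.5% | 2.27 | 5.94 | 0.967 |

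The Monte Carlo standard error of the shift is about 0.001. The standard error of the log rate ratio is about 0.16, so a 10-point imbalance moves it by log(1.067)/0.16 = 0.065/0.16, about 0.4 of a standard error. At rate 2 with dispersion 2, and at rate 6 with dispersion 1 or 4 (300 trials each), the 10-point shifts are 1.054 to 1.082 in one direction and 0.948 to 0.928 in the other.

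A separate set of large-sample fits (assumed rate 3 per year, ratio 0.8, dispersion 1.5, withdrawal uniform over 26 weeks) agrees. The rate is 59.3% too low with no withdrawal and about 62% too low with 15% in each arm, and the rate ratio is 0.806 under both offsets in each case.

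**The case against.** The strongest reply is that one generic sentence serves five endpoints and should be read endpoint by endpoint: for a maintenance count, the relevant time is the time in which such an episode can count. A careful programmer may well do that, and the SAP is based on the protocol that defines the window. But the clause rests on a defined term, and for the other three counts in the same sentence it must mean the whole period. So must the near-identical clause in the confirmatory models of SAP section 2.4.1: "the logarithm of the time period in which a hypoglycaemic episode is considered treatment emergent as offset". A second meaning for two of the five needs words that are not there. Even the generous reading leaves no rule for subjects without time after week 16.

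Several points on the other side stand:

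- Both endpoints are supportive. The primary test, the testing hierarchy and the confirmatory hypoglycaemia models are untouched.
- With equal early withdrawal the comparison does not move, and nothing in the documents points to an imbalance.
- That a modelled absolute rate will be reported for these two counts is inferred from the general statement on LSMeans. It is not stated for them specifically.
- The descriptive rate per 100 years has no spelled-out denominator for any endpoint, and no error in it is shown. The gap matters more for maintenance because two candidate periods exist.
- Restricting to subjects with time after week 16 departs from the general rule that "Analyses of all endpoints will be based on the Full Analysis Set (FAS"), since that subset is selected after randomisation.

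**Conclusion.** The concern holds. As written, the offset for the two maintenance-period models covers the wrong period, and the modelled rates are 59% too low for completers. That figure follows from the documents alone. With 5–25% withdrawal spread evenly over time (an assumption) it becomes 60–63%.

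The rate ratio is affected only if early withdrawal differs by arm: about 3% for a 5-point imbalance and 5–8% for a 10-point imbalance, under the simulation inputs above. This should be corrected before analysis, but no primary or confirmatory conclusion depends on it. What a programmer would actually have done cannot be known from the text.

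**What to change.** For the two maintenance endpoints only:

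1. Define the maintenance period in the SAP as Protocol section 4.2.3.2 does.
2. Set the offset to the log of each subject's treatment-emergent time from week 16 to last dose + 7 days.
3. Include FAS subjects with positive time in that window, and say that this subset is selected after randomisation. Say also whether subjects who stopped in the week before week 16, and so contribute only follow-up time, are included. The offset in item 2 includes them; in the 10%/10% simulation they numbered about 3 of 537, against about 50 with no time in the window.
4. Use the same exposure definition as the denominator of the descriptive maintenance rate per 100 years.

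Leave the other hypoglycaemia models as they are. The cost is one sentence in Protocol section 17.4.2.2, one in SAP section 2.4.3, one definition in the SAP and one derived variable. Data collection, sample size and confirmatory tests do not change.

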2.5 Interim analysis

No interim analyses or other analyses of unblinded data will be performed before the database is locked

2.6 Health economics and/or patient reported outcomes

The following questionnaires will be used to compare PROs and costs associated with hypoglycaemia between treatments:

- SF-36^{4,5}
- TRIM-D⁶ and TRIM-D Device⁶
- Device Specific Questionnaires I and II⁷

For the questionnaires , SF-36 and TRIM-D the change in score (total score if appropriate) from baseline will be analysed separately using an ANOVA method with treatment, anti-diabetic therapy at screening and sex as fixed factors, and age and the relevant baseline value as covariates.

For the device questionnaire TRIM-D Device , which is not assessed at baseline, the score (total score if appropriate) will be analysed using an ANOVA method with treatment, anti-diabetic therapy at screening and sex as fixed factors, and age as covariate.

For Device Specific Questionnaires I and II, since there are no validated scoring algorithms, formal statistical analysis will not be conducted and only descriptive statistics will be presented.

3 Changes to the statistical analyses planned in the protocol

There were 2 minor changes to the statistical analyses planned in the protocol as described below:

- The mean PG at baseline as covariate in the analysis for the 2-point SMPG profiles was not included since the 2-point SMPG was not collected until visit 3.
- Last Observed Value (LOV) was defined to summarise efficacy data and replace LOCF in summary table.

4 References

1. EMEA-Committee for Proprietary Medicinal Products. CPMP/EWP/482/99 - Points to consider on switching between superiority and non-inferiority. 27-2-2000.
2. Food and Drug Administration. Food and Drug Administration, Code of Federal Regulations, Guidance for Industry, Diabetes Mellitus: Developing Drugs and Therapeutic Biologics for Treatment and Prevention. Draft Guidance. 2008.
3. Rubin DB. Inference and missing data. *Biometrika* 1976; 63(3):581-592.
4. Ware JE, Jr., Sherbourne CD. The MOS 36-item short-form health survey (SF-36). I. Conceptual framework and item selection. *Med Care* 1992; 30(6):473-483.
